9.7 Prohibited medications and procedures

The medications listed in [Panel 7](#) are prohibited during the trial. In the case that any prohibited treatments are used during the trial, it must be recorded as a protocol deviation.

The following circumstances require permanent discontinuation of IMP:

- Use of any other biologic immunomodulating agent than IMPs.
- Use of any prohibited medication that in combination with IMP results in a significant risk to the subject's safety (as assessed by the investigator).
- Administration of a live vaccine.

If the prohibited medication does not require permanent discontinuation of IMP, then the investigator and the sponsor's medical expert should discuss and consider to either discontinue the prohibited medication or discontinue the IMP.

THIS DOCUMENT CONTAINS CONFIDENTIAL INFORMATION AND MUST NOT BE COPIED OR MADE AVAILABLE TO ANY THIRD PARTY WITHOUT THE PRIOR WRITTEN CONSENT OF THE LEO PHARMA GROUP

Panel 7: Prohibited medications and procedures

Prohibited medication/procedure	Prohibited from	Prohibited to
Etanercept ¹	2 weeks prior to first administration of IMP	Week 28
Adalimumab ¹	4 weeks prior to first administration of IMP	Week 28
Infliximab ¹	8 weeks prior to first administration of IMP	Week 28
Certolizumab pegol ¹	10 weeks prior to first administration of IMP	Week 28
Ustekinumab ¹	First administration of IMP	Week 28
Any other approved or experimental anti-IL-17 or anti-IL-23 ¹	Not allowed at any time	Week 28
Other experimental or commercially available biologic immunomodulator(s)	4 weeks or 5 half-lives, whichever is longer, prior to first administration of IMP	Week 28
Any other non-marketed drug substance	4 weeks or 5 half-lives, whichever is longer, prior to screening	Week 28
Ultraviolet A light therapy (with or without psoralen), ultraviolet B light therapy, excimer laser	4 weeks prior to first administration of IMP	Week 28
Oral retinoids; methotrexate; cyclosporine; systemically administered calcineurin inhibitors; azathioprine; thioguanine; hydroxyurea; fumarates; apremilast; or oral or parenteral corticosteroids including intramuscular and intraarticular administration (with the exception that: otic, nasal, ophthalmic, or inhaled corticosteroids within recommended doses are permitted).	4 weeks prior to first administration of IMP	Week 28
Topical therapies for psoriasis (e.g. calcineurin inhibitors and vitamin D analogues, super-potent or potent topical steroids) with the following exceptions: Upper mid-strength or lower potency topical steroids on the face, axillae, and groin only. Shampoos without steroids. Bland emollients without urea or beta or alpha hydroxy acids.	7 days prior to first administration of IMP	Week 28
Use of live vaccines ¹	4 weeks prior to first administration of IMP	Week 28

Abbreviations: IL = interleukin; IMP = investigational medicinal product.

1) Use requires permanent discontinuation of IMP.

THIS DOCUMENT CONTAINS CONFIDENTIAL INFORMATION AND MUST NOT BE COPIED OR MADE AVAILABLE TO ANY THIRD PARTY WITHOUT THE PRIOR WRITTEN CONSENT OF THE LEO PHARMA GROUP

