12. Subject has any suicidal ideation of severity 4 or 5 ('some intent to act, no plan' or 'specific plan and intent') based on the C-SSRS questionnaire at screening or baseline.
13. Subject has a PHQ-8 score of ≥ 10 , corresponding to moderate-to-severe depression at screening or baseline.
14. Subject has a history of depressive disorder with severe episode(s) within the last 2 years.
15. Subject has any concurrent medical condition that, in the opinion of the investigator, could cause the trial to be detrimental to the subject.

Laboratory abnormalities

16. Subject has laboratory abnormalities that, in the opinion of the investigator, will prevent the subject from completing the trial or interfere with the analysis of results, including:
 - White blood cell (WBC) count $< 3.00 \times 10^9 / L$.
 - Absolute neutrophil count (ANC) $< 2.00 \times 10^9 / L$.

THIS DOCUMENT CONTAINS CONFIDENTIAL INFORMATION AND MUST NOT BE COPIED OR MADE AVAILABLE TO ANY THIRD PARTY WITHOUT THE PRIOR WRITTEN CONSENT OF THE LEO PHARMA GROUP

- Aspartate aminotransferase (AST) or alanine aminotransferase (ALT) $>2\times$ the ULN (upper limit of normal).
- Serum direct bilirubin ≥ 1.5 mg/dL (≥ 25.7 μ mol/L).

Wash-out and prohibited medications

17. Subject has used potent topical steroids, topical anthralin/dithranol, topical calcipotriol, or any formulation or potency of topical therapy, within 7 days prior to first administration of IMP (exceptions are specified*).

* Upper mid-strength or lower potency topical steroids on the face, axillae, and groin; bland emollients (without urea or alpha or beta hydroxy acids); and shampoo without steroids are permitted.

18. Subject has used any of the following treatments* within 4 weeks prior to first administration of IMP.

* Ultraviolet A light therapy (with or without psoralen); ultraviolet B light therapy; excimer laser; oral retinoids; methotrexate; cyclosporine; systemically administered calcineurin inhibitors; azathioprine; thioguanine; hydroxyurea; fumarates; apremilast; oral or parenteral corticosteroids including intramuscular or intraarticular administration; or any other immunomodulating therapy for psoriasis or any other indication (otic, nasal, ophthalmic, or inhaled corticosteroids within recommended doses are permitted).

19. Subject has received any of the following biologic immunomodulating therapies prior to first administration of IMP:

Approved agents:

- Within 2 weeks for etanercept.

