9.6 Concomitant medication and concurrent procedures

Any medication or vaccine that the subject receives throughout the trial (including screening period) must be recorded in the subject's medical record and the eCRF along with details such as:

- Medication name.
- Indication.
- Start and stop date of administration (it will also be recorded if the medication is ongoing).
- Dosage information, including dose, unit, and frequency.
- Route of administration.

Similarly, any concurrent procedure must also be recorded in the subject's medical record and the eCRF. The following details will be recorded:

- Procedure.
- Body location (if relevant).
- Indication.
- Start and stop date (it will also be recorded if the procedure is ongoing).

Investigators may prescribe concomitant medications or treatments to provide adequate supportive care as deemed necessary, except for medications listed in Section 9.7. The sponsor's medical expert should be contacted if there are any questions regarding concomitant or prior therapy.

THIS DOCUMENT CONTAINS CONFIDENTIAL INFORMATION AND MUST NOT BE COPIED OR MADE AVAILABLE TO ANY THIRD PARTY WITHOUT THE PRIOR WRITTEN CONSENT OF THE LEO PHARMA GROUP

The following concomitant medications related to psoriasis treatment are permitted throughout the trial (including the screening period):

- Upper mid-strength or lower potency topical steroids on the face, axillae, and groin only.
- Shampoos without steroids.
- Bland emollients without urea or beta or alpha hydroxy acids.

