5.4.1.2.3 Robustness with respect to use of prohibited medication and procedures

These sensitivity analyses will assess the robustness of the results of the main analysis with respect to the assumption that use of prohibited medication and procedures, cf. CTP Panel 7, has no influence on the endpoint of interest among subjects not discontinuing IMP. This will be done by excluding data collected after use of prohibited medication and procedures. Missing data resulting from such exclusions will be imputed in separate sensitivity analyses based on each of the following imputation algorithms:

- Non-responder imputation.
- ‘Delta-adjusted’ pattern-mixture model.

For subjects using prohibited medication and procedures or experiencing intercurrent events to be addressed by ‘composite’ or ‘hypothetical’ strategies cf. [Panel 11](#), the data observed after the occurrence of such events will be excluded from the imputation models.

Following these exclusions, multiple imputation of missing scores will be done just as in the main analysis (including the use of the same seeds) for missing data, which

- did not arise after use of prohibited medication and procedures, or
- did arise after use of prohibited medication and procedures that happened after the occurrence of intercurrent events to be addressed by ‘composite’ or ‘hypothetical’ strategies (i.e. the value of the estimand’s variable will in such a case be determined by the strategy for addressing the intercurrent event).

THIS DOCUMENT CONTAINS CONFIDENTIAL INFORMATION AND MUST NOT BE COPIED OR MADE AVAILABLE TO ANY THIRD PARTY WITHOUT THE PRIOR WRITTEN CONSENT OF THE LEO PHARMA GROUP

For the sensitivity analysis based on non-responder imputation, all binary response values corresponding to missing data arising after use of prohibited medication and procedures that did not happen after the occurrence of intercurrent events to be addressed by ‘composite’ or ‘hypothetical’ strategies, will be imputed as non-responses.

For the sensitivity analysis based on ‘delta-adjusted’ pattern-mixture models, imputed scores will, as described in section 5.4.1.2.1, be adjusted by a specified margin Δ (Panel 13) for missing scores arising after use of prohibited medication and procedures that did not happen after the occurrence of intercurrent events to be addressed by ‘composite’ or ‘hypothetical’ strategies.

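### Panel 7 omits the open class of immunomodulating therapy that exclusion 18 bars at entry, so the prohibited-medication sensitivity analysis, which takes its list from Panel 7, cannot remove responses that follow such a drug

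*Protocol*

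**What the plan says.** **Before first IMP.** Protocol Section 8.3, exclusion 18, lists systemic and light therapies barred for 4 weeks and closes with an open class: "or any other immunomodulating therapy for psoriasis or any other indication".

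**After first IMP.** Protocol Section 9.7, Panel 7, governs the period to Week 28. Its systemic non-biologic row is a closed list: "Oral retinoids; methotrexate; cyclosporine; systemically administered calcineurin inhibitors; azathioprine; thioguanine; hydroxyurea; fumarates; apremilast; or oral or parenteral corticosteroids", with the usual exceptions for local corticosteroids. Two other rows are open-ended. One covers other biologic immunomodulators, the other "Any other non-marketed drug substance".

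**Other medication rules.** Section 9.5 bans rescue medication for the whole trial. Section 9.6 names three kinds of permitted psoriasis medication (limited topical steroids, steroid-free shampoos, bland emollients). It also states: "Investigators may prescribe concomitant medications or treatments to provide adequate supportive care as deemed necessary, except for medications listed in Section 9.7". Under Section 9.7, use of a prohibited treatment is a protocol deviation.

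**Analysis.** SAP 5.3 defines three intercurrent events: two kinds of permanent IMP discontinuation, and unblinding. Other medication is handled only in SAP 5.4.1.2.3 (sensitivity analysis 3 in Protocol 14.3.6.2), which is scoped as "use of prohibited medication and procedures, cf. CTP Panel 7".

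**Biologics.** The text of Section 9.7 requires permanent IMP discontinuation for "Use of any other biologic immunomodulating agent than IMPs". Footnote 1 of Panel 7 carries that consequence for the named biologics, but the row for other biologic immunomodulators has no footnote mark.

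**The concern.** SAP 5.4.1.2.3 asks whether the result depends on responses reached with the help of another treatment. Amendment 1 added this analysis after regulatory input. It can only do its job if its medication set holds the drugs that could clear skin.

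The protocol treats the open class in exclusion 18 as important enough to keep out at entry, for any indication. The same class is missing from the list that drives the analysis. A reason to start such a drug during the trial is conceivable: psoriatic arthritis and other immunoinflammatory diseases are recorded at entry (Section 11.2.2) and psoriatic arthritis is not an exclusion. JAK inhibitors, for which Section 11.2.3 records contraindications, do not appear in Panel 7.

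At stake is the meaning of a reassuring sensitivity result, which could come from the analysis not looking at the relevant drugs. Recording is affected too. Section 9.7 makes use of a listed drug a deviation and, where IMP need not be stopped, calls for a discussion with the sponsor's medical expert. Neither provision is triggered by an unlisted drug.

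**Working it through.** The point rests on reading the passages together. The plan gives no figure to reproduce.

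**Step 1. Which therapies are listed, and when.**

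| Therapy | Before first IMP | Panel 7, to Week 28 | In SAP 5.4.1.2.3 set |
|---|---|---|---|
| Named systemic drugs, e.g. methotrexate, apremilast | Barred (exclusion 18) | Listed | Yes |
| Other biologic immunomodulators | Barred (exclusion 19) | Listed, no discontinuation footnote | Yes |
| Non-marketed substances | Barred (exclusion 23) | Listed | Yes |
| Marketed, unlisted non-biologic immunomodulator, for psoriasis | Barred (exclusion 18) | Not listed; 9.5 and the 9.6 list of permitted psoriasis medication point against use | No |
| The same, for another indication | Barred (exclusion 18) | Not listed; 9.6 permits supportive care not listed in 9.7 | No |

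The last two rows are the gap. Only the last is free of conflicting text.

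**Step 2. How a Week 16 PASI 100 is scored after other medication.** The composite variable in SAP 5.4.1 is 1 for a PASI 100 responder who has not permanently discontinued IMP independently of pandemic restrictions, and 0 otherwise.

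| Subject with PASI 100 at Week 16 | Main analysis | SAP 5.4.1.2.3, non-responder version |
|---|---|---|
| On IMP, earlier use of a listed drug such as methotrexate | 1 | 0 |
| On IMP, earlier use of an unlisted immunomodulator | 1 | 1 |
| Stopped IMP before Week 16, not for pandemic reasons, either drug | 0 | 0 |

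The first two rows agree in the main analysis and differ only in the sensitivity analysis. In its delta-adjusted version, the first subject's score is excluded, imputed and shifted, while the second subject's observed score stays. Time to PASI 100 (SAP 5.4.2) has no prohibited-medication rule, so listed and unlisted drugs are handled alike there.

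**Step 3. Scale.** One response in an arm of 120 is 1/120 = 0.83 percentage points. SAP Section 6 records a decision to end the trial ahead of schedule. If an arm holds fewer than 120 subjects, each response weighs more. The documents give no rate of such drug use.

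**Step 4. The biologics row.** A site following the 9.7 text stops IMP, and if this happens before Week 16 the subject scores 0. A site relying on the unmarked Panel 7 row could take the route of discussing whether to stop the drug or IMP, so IMP might continue and the subject could score 1 in the main analysis. SAP 5.4.1.2.3 would still catch this case, because the row is in Panel 7.

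**The case against.** The best reply is that the gap is narrow. Biologics, methotrexate, cyclosporine, azathioprine, apremilast, systemic corticosteroids and non-marketed drugs are all listed. Section 9.5 bans rescue, Section 9.6 names only three permitted psoriasis medications, and its general permission is for supportive care, with questions sent to the sponsor's medical expert. This stands. A reader might infer from Panel 7 alone that any unlisted immunomodulator is allowed on trial. For psoriasis the documents do not support that; they are ambiguous. For another indication, 9.5 and the list of permitted psoriasis medication do not close the gap.

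A second reply is that adding the missing class to Panel 7 would leave the primary result untouched. This also stands. A reader might infer that the omission lets contaminated responses count throughout the analyses. It does not: the main analysis and time to PASI 100 count responses after listed drugs as well while IMP continues, and non-pandemic IMP discontinuation before Week 16 scores 0 whatever else was taken.

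A third reply is that no harm is shown. The documents give neither frequency nor arm. A reader might infer a loss of power or a diluted treatment difference. That would concern the primary test, which the omission does not alter, and the direction would depend on the arm in which the extra responses fell.

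On the biologics row, it is fair to say that the 9.7 text already states the rule. The panel should still agree with it, because discontinuation is part of the primary variable.

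**Conclusion.** The mismatch between exclusion 18 and Panel 7 is plain in the text, and it carries into SAP 5.4.1.2.3. Followed as written, the only analysis meant to test the influence of other medication keeps PASI 100 responses that follow a marketed, unlisted, non-biologic immunomodulator in subjects still on IMP. The clear case is use for an indication other than psoriasis; use for psoriasis is ambiguous.

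The consequence is limited to the scope of that sensitivity analysis and to deviation recording under Section 9.7. Its size is 0.83 points per affected response at 120 per arm, multiplied by a number of responses that the documents do not give and that may be zero. No direction can be claimed.

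The missing footnote on the biologics row is a separate, smaller inconsistency that could lead sites to differ on whether IMP is stopped.

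**What to change.** 1. In SAP 5.4.1.2.3, define the medication set as Panel 7 plus any therapy named or caught by exclusion 18, keeping that criterion's stated corticosteroid exceptions. Turn the open class into an explicit drug list before unblinding. Section 9.6 already has medication name, indication and dates recorded, so no new data are needed. This is a cheap improvement; the downside is slightly more data excluded and imputed in a sensitivity analysis. It is an analysis definition and does not depend on what the protocol ends up permitting.

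2. In the protocol, reconcile exclusion 18, Sections 9.5 and 9.6, and Panel 7, so that the status of an unlisted immunomodulator after first IMP is clear for psoriasis and for other indications. Reconcile the Panel 7 row for other biologic immunomodulators with the discontinuation text of Section 9.7. Which treatments are prohibited, and which require stopping IMP, is for the sponsor to decide. The cost is a few words of protocol text or, if the protocol is no longer being amended, a clarifying note in the SAP and trial report on how the passages were read.

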9.8 Treatment logistics and accountability

9.8.1 Labelling and packaging of trial products

The IMP will be packaged in individually numbered kits.

The labelling of IMPs will be in accordance with the EU Guidelines for good manufacturing practices for medicinal products for human and veterinary use, Annex 13 (19), local regulations, and trial requirements. Label text will be translated into local languages, as required.

9.8.2 Storage of trial products

All LEO Pharma supplied IMPs (Section 9.1) must be stored in a secure and restricted area under the conditions specified on the label and remain in the original container until dispensed.

The IMPs must be stored at 2–8°C (and protected from light) at the trial site. Do not freeze the IMPs. The pre-filled syringes must not be shaken or heated.

The temperature during storage should be monitored by a calibrated, stationary, and continuously monitoring system. Minimum requirement is a calibrated min/max thermometer. A temperature log must be kept to document the storage within the right temperature interval, unless the temperature recorder has back-up of data. Storage facilities should be checked at least every working day.

Storage of IMP may be delegated, e.g. to a hospital pharmacy, as locally applicable.

Note that in the cases listed below, site staff should not use the affected IMP and should immediately quarantine the IMP (also change the status in the IRT system), and contact their clinical research associate (CRA) for further guidance:

- Temperature excursion upon receipt or during storage at the trial site.
- Damaged syringe or kit.

Damaged IMP should be documented in the IRT system and reported as a product complaint to Global Safety, LEO Pharma (see Section 9.10). Damaged IMP may not be used.

Further details regarding IMP storage (including handling of temperature excursions upon receipt or during storage at the trial site) and handling of damaged IMP (including kits damaged upon receipt) are provided in the trial product handling manual.

THIS DOCUMENT CONTAINS CONFIDENTIAL INFORMATION AND MUST NOT BE COPIED OR MADE AVAILABLE TO ANY THIRD PARTY WITHOUT THE PRIOR WRITTEN CONSENT OF THE LEO PHARMA GROUP

9.8.3 Drug accountability

The investigator is fully responsible for the IMPs at the trial site and for maintaining adequate control of the IMPs and for documenting all transactions with them.

Dispensing of IMPs may be delegated, e.g. to a hospital pharmacy, as locally applicable.

An individual drug accountability form must be kept of the IMP dispensed/administered to each subject randomised in the trial. This individual drug accountability form must be available during monitoring visits and will be checked by the CRA to verify correct dispensing of the IMP. Drug accountability information will be entered in the IRT system, where also inventory status of all IMP at the trial site will be maintained. Refer to the IRT manual for information on how to update the kit status in the IRT system.

The trial site will maintain trial kit cartons from used kits until reconciliation has been checked by the CRA. Subsequently, the trial kit cartons from used kits may be discarded.

All unused IMP (including packaging material) supplied by the contract manufacturing organisation (CMO) on behalf of LEO Pharma will be returned to the CMO. Prior to return, the IMP must be fully accounted for by the CRA with the help of site staff responsible for dispensing the IMP. Accountability must be documented in the IRT system. Please refer to the trial product handling manual for further details.

9.8.4 Treatment compliance

IMP injections will be performed by site staff. Site staff will also keep the accountability records up to date. Treatment compliance will be assessed by the site staff at the time points specified in Section 4. Any non-compliance (subject received partial dose; subject received no dose) and the reason for it must be recorded in the eCRF.

9.8.5 Trial product destruction

Used syringes can be destroyed at the trial site provided the trial site has procedures in place for such IMP destruction. Trial sites that do not have such IMP destruction procedures in place will dispose used IMP in sharps bins that will be returned to the CMO. For more information, see the trial product handling manual.

Unused IMP and disposal containers with used syringes returned to the CMO will be destroyed by the CMO according to approved procedures and any local requirements.

THIS DOCUMENT CONTAINS CONFIDENTIAL INFORMATION AND MUST NOT BE COPIED OR MADE AVAILABLE TO ANY THIRD PARTY WITHOUT THE PRIOR WRITTEN CONSENT OF THE LEO PHARMA GROUP

9.9 Provision for subject care following trial completion

To ensure appropriate treatment of the subjects after they have completed the trial, the subjects will be treated at the investigator's discretion or referred to other physician(s) according to standard practice.

9.10 Reporting product complaints

Any defects or issues with the IMP as well as any device deficiency (including malfunctions, use errors, and inadequate labelling) must be reported to Global Safety at LEO Pharma on the trial-specific complaint form (paper) within 3 days of first knowledge.

Critical complaints (defined as any defect, issue, or device deficiency that has or potentially could have a serious impact for the subject, such as SAE or large particles in the syringe) must be reported to Global Safety, LEO Pharma within 24 hours.

Complaint forms should contain a detailed description of the defect, issue, or device deficiency, including whether it led to an AE. (S)AEs which occur due to a defect or issue with the IMP or due to a device deficiency will be reported by the investigator as described in Sections [13.3](#) and [13.4](#).

Refer to the trial product handling manual for information on how to update the kit status in the IRT system.

During the investigation of the product complaint, the IMP or device must be stored at labelled conditions unless otherwise instructed; the trial site will be notified whether the IMP or device needs to be returned for further investigation or may be destroyed.

Global Safety, LEO Pharma contact information for reporting product complaints:

[contact]

E-mail address: [contact]

THIS DOCUMENT CONTAINS CONFIDENTIAL INFORMATION AND MUST NOT BE COPIED OR MADE AVAILABLE TO ANY THIRD PARTY WITHOUT THE PRIOR WRITTEN CONSENT OF THE LEO PHARMA GROUP

10 Discontinuation and withdrawal

